## Study Information

Title	Real-world effectiveness of different COVID-19 vaccines in Spain: a cohort study based on public electronic health records (BIFAP)
Protocol version identifier	1.0
Date of last version of protocol	20 april 2021
EU PAS Register number	Study not yet registered
Active substance	
 
1. Vacuna de ARNm frente a COVID- 19 (con nucleósidos modificados)
 
2. Vacuna de ARNm frente a COVID-19 (con nucleósidos modificados)
 
3. (ChAdOx1-S [recombinant]) made up of another virus (of the adenovirus family)
 
4. Recombinant, replication-incompetent adenovirus type 26 (Ad26) vectored COVID-19 vaccine (Ad26.COVS-S [recombinant])
 

Medicinal product	
 
1. Comirnaty concentrado para dispersión inyectable
 
2. COVID-19 Vaccine Moderna, dispersión inyectable
 
3. VAXZEVRIA suspension inyectable
 
4. COVID-19 Vaccine Janssen suspension for injection
 

Product reference	-
Procedure number	-
Marketing authorisation holder(s)	
 
1. Biontech Manufacturing GmbH
 
2. Moderna Biotech Spain
 
3. Astrazeneca
 
4. Janssen
 

Research question and objectives	To evaluate the effectiveness of COVID-19 vaccines (i.e. comirnaty, Moderna's, Vaxzevria and Janssen and subsequent authorised vaccines) in preventing COVID-19 diagnosis.
Country(-ies) of study	Spain
Author	
[name]
 
The current protocol is based on recommendations included in the following protocol template: Layton B, Garcia X. et al. Real-world effectiveness of <<COVID-19 vaccine product>> in Europe: a protocol template for a cohort study based in existing health care data sources from the ACCESS project

## Trademarks

Brand Name	Generic Name	Trademark Holder
Comirnaty	Vacuna de ARNm frente a covid	Biontech Manufacturing GmbH
COVID-19 Vaccine Moderna	Vacuna de ARNm frente a covid	Moderna Biotech Spain
COVID-19 Vaccine Oxford	(ChAdOx1-S [recombinant]) made up of another virus (of the adenovirus family)	Astrazeneca
COVID-19 Vaccine Janssen	Recombinant, replication- incompetent adenovirus type 26 (Ad26) vectored	Janssen
Any other covid-19 vaccine approved during the study period		

## 2 List of Abbreviations

AEMPS	Spanish Agency for Medicines and Medical Devices
BIFAP	Base de datos para la Investigación Farmacoepidemiológica en Atención Primaria
CI	confidence interval
COVID-19	illness caused by the SARS-CoV-2 (severe acute respiratory syndrome coronavirus 2) virus
eHR	electronic health records
EMA	European Medicines Agency
ENCePP	European Network of Centres for Pharmacoepidemiology and Pharmacovigilance
EU PAS Register	European Union Electronic Register of Post-Authorisation Studies
GPP	Good Pharmacoepidemiology Practices
GVP	Good Pharmacovigilance Practices
HCU	health care utilisation
HR	hazard ratio
ICPC-2	International Classification of Primary Care, 2nd Edition
ICD-9	International Classification of Diseases, 9th Revision
ICD-10	International Classification of Diseases, 10th Revision
ICU	intensive care unit
IRR	incidence rate ratio
ISPE	International Society for Pharmacoepidemiology
PASS	postauthorisation safety study
RD	risk difference
RR	risk ratio
STROBE	Strengthening the Reporting of Observational Studies in Epidemiology

## 4 Abstract

**Title:** Real-world effectiveness of different COVID-19 vaccines in Spain: a cohort study based in primary health care (BIFAP) and linked data sources

**Rationale and background:** Multiple vaccine candidates for COVID-19 are progressing through development and testing with anticipated widespread adoption and use after approval. The real-world effectiveness of these vaccines must be evaluated in populations in Spain.

**Research question and objectives:** To evaluate the effectiveness of all COVID-19 vaccines administered in Spain in reducing the medically attended diagnosis of COVID-19 in any setting (confirmed through test and regardless the prognosis and clinical phenotype)

Secondary objectives of this study will be splitting the effectiveness

- by the following outcomes:
  - asymptomatic (defined as a positive test (whether PCR or antigens) without recorded symptoms in primary care +-14days of the date the sample was taken). Note: In epidemiological vigilance protocols, among asymptomatic patients, isolation must be maintained till 10 days after the date when the sample was taken.
  - symptomatic (defined as a positive test (whether PCR or antigens) with recorded symptoms in primary care or Hospitalisations/Intensive care unit (ICU) admissions +-14days of the date the sample was taken (or at anytime linked with the test result))
  - Hospitalisations/Intensive care unit (ICU) admissions for COVID-19 at anytime linked with the test result or within +-14days of the date the sample was taken (if hospitalisation was recorded in primary care clinical profile)
  - All-cause mortality as linked with the test result or within +-14days of the date the sample was taken (if hospitalisation was recorded in primary care clinical profile)
- over clinically meaningful subgroups (old people; patients with cardiovascular disease, diabetes, or chronic pulmonary disease, chronic renal impairment, treated cancer, patients with a history of transplantation, Down Syndrome found linked with the prognostic of the covid-19 infection; as well as smoking, males and obesity suspected linked with the prognosis in some studies)
- along the time since complete vaccination (3 months, 6 months and ever after).

**Study design:** This is an observational cohort study to compare the occurrence of covid-19 infection among unvaccinated and vaccinated individuals.

**Population:** Individual aged  $\geq 18$  years with at least 1 year of record with their primary care physician from December 2020 till April 2021.

**Variables:**

- COVID-19 vaccinations will be identified from a vaccination registry linked with each patient's primary care clinical history.
- Medically attended diagnosis of COVID-19 in any setting will be identified through linked registries of 1) COVID positive test results, 2) hospital COVID diagnosis or discharged COVID diagnosis.
- Covariates will be collected from primary care eHR. Covariates will include demographic information, morbidities, medication use, health care utilisation, markers of current disease status at time zero, and markers of frailty.

**Data sources:** Base de datos para la Investigacion farmacoepidemiológica en Atención Primaria (BIFAP) and linked registries of 1) COVID positive test results, 2) hospital COVID diagnosis or 3) discharged COVID diagnosis

**Study size:** BIFAP database includes up-to-standard information for around 7.7 million patients aged  $\geq 18$  years.

**Data analysis:** Characteristics of the vaccinated and unvaccinated groups at baseline will be described. Incidence rates of COVID-19 outcomes will be calculated and compared between the two groups, and vaccine effectiveness measures will be estimated by 1 minus the hazard ratios (HR; 95%CI). Additional time period-specific effect estimates (e.g., at 3, 6, or >6 months after vaccination) will also be estimated.

Stratified analysis will separately estimate vaccine effectiveness in clinically meaningful subgroups and calendar periods. Sensitivity analyses will evaluate the robustness of the study approach across variations of the study methodology.

**Milestones:** Evaluation of the availability of data will start during 1-15 June but timelines may be impacted by the date the data are received from the different regions and BIFAP common data model is ready for evaluation (End of July).

## 5 Amendments and Updates

None to date.

## 6 Milestones and Timeline

Milestone	Date
Approvals by ethics and scientific review bodies	March 2021
Start of data collection a	End of June 2021
End of data collection b	July 2021
<Study progress report(s) 1>	August 2021
<Study progress report(s) 2>	September 2021
<Study progress report(s) 3>	December 2021
<Interim report 1>	
<Interim report 2>	
<Interim report 3>	
Registration in the EU PAS Register	April 2021
Final report of study results	April 2022

EU PAS Register = European Union Electronic Register of Post-Authorisation Studies.

Note: Timelines may be impacted by approvals of ethics and scientific review bodies, and availability of data and staff at research institutions once contracts and approvals are finalised.

a Start of data collection is “the date from which information on the first study subject is first recorded in the study data set or, in the case of secondary use of data, the date from which data extraction starts” [1].

b End of data collection is “the date from which the analytical data set is completely available” [1].

## **7 Rationale and Background**

COVID-19, the disease caused by the novel coronavirus SARS-CoV-2, has become a global pandemic, affecting countries throughout Europe and the world. At the time of writing of this protocol, three vaccines are being administered in Spain (i.e. Comirnaty and COVID-19 vaccine Moderna) and two approved (Astrazeneca-Oxford and Janssen's) after conditional marketing authorisation by EMA (after granting of the EU Commission on 21st December, 6th January, 29th January, and 11th March 2021 respectively). The real-world effectiveness of these vaccines must be evaluated in Spanish population.

This is an observational cohort study, including patient-level real-world evaluation of the effectiveness of the different COVID-19 vaccines administered in Spain (not ecological evaluation). The secondary data included in the Base de datos para la Investigación Farmacoepidemiológica en Atención Primaria (BIFAP; the Spanish Database for Pharmacoepidemiological Research in Primary Care) will be used [65, 67].

New emerging data on covid infections and vaccinations will not be validated since we will be working with the gold-standard data considered today (i.e. lab results registries for covid infection and vaccinations respectively).

BIFAP has been previously validated for research in pharmacoepidemiology, including the estimations of the precision of several clinical outcomes [65] that will be covariates of the current study (such as cardiovascular/digestive/endocrinological outcomes). Also, vaccination recorded in BIFAP's Table of Vaccines has also been validated [66] that will include the linked official covid vaccinations. The algorithm for maximizing the precision and sensitivity will be utilised for the covariates collection.

As receipt of a newly licenced vaccine may be strongly associated with risk status (e.g., health care workers or essential workers), health status (e.g., at high risk for complications), or lifestyle factors (e.g., adherence to recommendations regarding vaccination, hygiene, self-quarantine, social distancing, and/or mask-wearing), confounding is likely the strongest threat to the validity of an observational study [3-9].

We intent to address confusion through study design (e.g., restriction to scheduled people by calendar time, identifying exchangeable comparison groups/moments) and analysis (e.g., statistical adjustment and stratification).

This protocol is based on a template that outlined a general approach to designing and implementing a comparative study of the effectiveness of a newly approved COVID-19 vaccine using existing health care databases [68].

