#### **COVID-19 Test results (PCR, antigens, etc.)**

Test results for coronavirus will be linked with PC eHR. For effectiveness analysis, cases will be positive covid infections recorded in that registry that may be confirmed through positive PCR, Antigens or any other confirmatory criteria established by clinical protocols (that definition is out of the scope of the current study).

Laboratory-confirmed infection is considered gold-standard to identify cases for the main analysis, thus no predictive values will be estimated. As explained below, identification of so-called 'possible' covid cases recorded only through diagnosis coding (without lab information) will be performed in a Sensitivity analysis (Section 9.7.4.2).

Also, an estimation of the concordance between the observed incidences in BIFAP and those 'expected' will be performed (i.e. external validation) as a proxy for the accurateness to identify cases in BIFAP and discussion of potential reasons if differences would be present.

The 'expected' cumulative incidences will be calculated by dividing the COVID cases reported daily to RENAVE (base de datos de vigilancia epidemiológica; by calendar period, region and age) by the population reported in the Spanish National Statistics Institute for that year [73]. Access to RENAVE will be available by one of the institution collaborating in the current study [74].

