### **9.1.1.3 Validity of Vaccine Exposure**

The precision and sensitivity of COVID-19 vaccine records included in the BIFAP's Table of Vaccine are not known. However, high precision and sensitivity have been estimated for other vaccinations recorded in that table

- after manual revision (against free text comment for human papillomavirus vaccination)(2) or
- validated against expected coverages (as in the Spanish recommended schedules) or external sources (such as other European countries with public

vaccination programs) for vaccinations against human papillomavirus, pertussis, influenza or meningococcus (3).

The information about the COVID vaccinations included in that Table is the result of linking all vaccination registries with the public PC eHR. That link has been strongly recommended (and it is compulsory) by the Ministry of Health and it is used by the Ministry to provide the official coverages since the vaccination campaigns started.

Vaccination data for each patient will include the vaccination date, dose, name of the vaccine, brand and batch for each jab.

Even though, the vaccinations records of the initial priority population for vaccination (i.e. frontline health and social care workers, residents in a care home and patients with special needs) will be available in BIFAP, we will not study them since we expect not enough quality criteria of the baseline consultations to the PCP. Thus, as aforementioned the current study will be restricted to populations where both, vaccination status and baseline and updated clinical history, can be accurately identified.

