### 9.3.1 Exposure Assessment and Time At Risk

Data will be collected from BIFAP database with data from Spain (described in [Data Sources](#)).

**Inclusion criteria** to the Source population: up-to-standard,  $\geq 1$  year baseline information in January 2021 in BIFAP. The last date of filling all the inclusion criteria will be the inclusion date. No restriction to age or sex will be applied.

**Exclusion criteria:** Patients with prevalent COVID vaccinations or infections ever before (i.e. washout period) the inclusion criteria will be excluded.

**Stop date:** the last moment of the following criteria will define the stop date to contribution: covid-19 infection, death, loss to follow-up and end of study period (the last date available in the data source at data collection).

**Exposure assessment:** The 1st vaccination recorded after the inclusion date will be the time zero for patients included in the vaccinated group, as explained in section 'Definition of Time Zero' [9.1.1.4](#).

From the source population, 10 individuals unvaccinated on or before time zero of the vaccinated pair (10:1) will be randomly selected among those with similar birth cohort, sex and region (matched criteria). Patients included in the comparison group, may be vaccinated later during their follow-up period and then contribute to the vaccinated group (from the date of vaccine administration ahead; i.e. time zero for the vaccinated group).

\*Note: All individuals vaccinated during their follow-up contribution will be included in the vaccinated group. While, a random selection of the unvaccinated individuals will be included as unvaccinated group.

The date and type of vaccine administered will be collected from the **Table of Vaccine** from BIFAP data model. In particular, Covid-19 vaccinations will be ascertained from official covid-19 vaccination registries and provided by the regional governments. The coding system is not known yet. The feasibility analysis will include an evaluation of the coding type, whether or not vaccines are recorded according to standardised system or not. We expect that either ATC07 (J07????) or National Code (CNF [Código Nacional de

Farmacia]) specific for pharmaceuticals in Spain is available for all vaccines administered.

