### **9.7.3 Comparative Analysis**

#### **9.7.3.1 Estimation of Vaccine Effectiveness**

Cox proportional hazards regression, yielding a hazard ratio (HR; 95%CI), accounting for censoring, changing incidence over time, and competing risks (Section 9.7.3.3) will be estimated for the defined periods: i.e. 0 to 14 days after D1, 15 after D1 until D2, 0 to 14 days after D2 and 15-90 days, 91-180 days, and  $\geq 181$  days after D2 in comparison with similar followed periods from time zero in the unvaccinated group.

This method will calculate a single vaccine effectiveness measure for each period of observation (assumed constant over those defined periods) in vaccinated versus unvaccinated groups. Crude vaccine effectiveness will be calculated for all the outcomes as 1 minus HR.

The assumption of proportionality of the survival curves in the vaccinated and unvaccinated groups will be evaluated.

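### The completeness of the linked COVID-19 vaccination records is never checked, so unlinked vaccinees stay in the comparator pool and pull VE toward zero, more so as coverage rises

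*Protocol*

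**What the plan says.** Section 7 of the protocol: "New emerging data on covid infections and vaccinations will not be validated since we will be working with the gold-standard data considered today". The sentence goes on to name the registries as that standard.

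Section 9.1.1.3, on the table that supplies the exposure: "The precision and sensitivity of COVID-19 vaccine records included in the BIFAP's Table of Vaccine are not known". It then cites validations of other vaccines in the same table and explains where the COVID-19 records come from: "The information about the COVID vaccinations included in that Table is the result of linking all vaccination registries with the public PC eHR". It describes the link as compulsory and adds that "it is used by the Ministry to provide the official coverages since the vaccination campaigns started".

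For infections, which are also called gold standard, section 9.1.1.2 plans an external check: "an estimation of the concordance between the observed incidences in BIFAP and those 'expected' will be performed". Section 9.7.4.3 repeats it, by region, calendar date and age. Vaccination coverage has no counterpart.

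Section 9.3.1 forms the comparator group: "10 individuals unvaccinated on or before time zero of the vaccinated pair (10:1) will be randomly selected". Comparators "may be vaccinated later during their follow-up period and then contribute to the vaccinated group". Section 9.7.3.1 sets each window after vaccination "in comparison with similar followed periods from time zero in the unvaccinated group". Duration of effect after complete vaccination is a secondary objective (section 8).

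**The concern.** In practice, unvaccinated means having no recorded dose. A vaccinated person whose registry entry did not reach the primary care record can be drawn as a comparator. That person never moves to the vaccinated group, because only a recorded dose triggers the move. Correctly linked vaccinees leave the pool, so the unlinked become a growing share of those who remain. The comparator group's infection rate falls and VE is understated, increasingly so at later calendar time and in regions with poorer linkage. The later windows after dose 2 lie later in calendar time, so part of this could be read as loss of protection.

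The planned looks at vaccination data do not reach the problem. The feasibility review of coding type (9.3.1) and the description of dose intervals (9.3.1) act on records that exist. Section 9.7.5 deals with missing date, brand or dose order and mentions external dose data only as an option for that purpose. Section 9.1.1 lists data validity as a feasibility item and points to 9.1.1.3, but that section sets out no check of COVID-19 records. Section 9.9 admits exposure misclassification in general terms, without direction or size.

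**Working it through.** **The plan's own figure.** Table 1 gives a probability of 1 that the upper 95% limit of the RR is below 1. For RR 0.05 at 1:1, each group has 7,720,843/2 people. Expected cases are 3,860,421.5 × 0.0006057 = 2,338.3 unexposed and 2,338.3 × 0.05 = 116.9 exposed. SE(ln RR) ≈ √(1/116.9 + 1/2,338.3) = 0.095, and 2.996/0.095 − 1.96 ≈ 29.6, so the probability is 1.000. All eight rows reproduce. The probability stays at 1.000 with 90% coverage and 90% linkage sensitivity. The issue is therefore bias, not power.

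**Contamination of the pool.** Let c be true coverage in the matched cell and s the probability that a vaccination is linked. The documents give neither, so the values below are assumptions. I also assume no false vaccination records, linkage loss unrelated to infection risk, and the same VE in unlinked as in linked vaccinees.

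- Truly vaccinated share of the recorded-unvaccinated: f = c(1−s)/(1−cs)
- Apparent VE = 1 − (1−VE)/(1 − f·VE)

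Example with c = 0.90, s = 0.97, VE = 70%: f = 0.027/0.127 = 21.3%; apparent VE = 1 − 0.30/(1 − 0.70 × 0.213) = 64.8%.

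| c | s | f | true VE 70% | true VE 95% |
|---|---|---|---|---|
| 30% | 0.99 | 0.4% | 69.9% | 95.0% |
| 30% | 0.95 | 2.1% | 69.6% | 94.9% |
| 90% | 0.99 | 8.3% | 68.2% | 94.6% |
| 90% | 0.97 | 21.3% | 64.8% | 93.7% |
| 90% | 0.95 | 31.0% | 61.7% | 92.9% |

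Table 1 expects VE from 66.9% to 95%, so the two columns roughly span the plan's range. The distortion is largest for the vaccines with lower VE.

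**Level shift or apparent waning.** I averaged over the planned windows with constant true VE, a linear rollout and dose 2 assumed at day 21. Each entry shows apparent VE at 15–90 days, then at 91–180 days after dose 2.

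| Rollout | s | true VE 66.9% | true VE 95% |
|---|---|---|---|
| 180 days to 80% | 0.95 | 64.3 → 63.0 | 94.4 → 94.1 |
| 180 days to 95% | 0.99 | 64.9 → 63.3 | 94.6 → 94.2 |
| 180 days to 95% | 0.95 | 59.5 → 52.6 | 93.2 → 91.3 |
| 60 days to 95% | 0.95 | 51.8 → 50.9 | 91.0 → 90.7 |

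In a quick rollout nearly all the bias is already present in the 15–90 day window. A visible false decline needs a slow rollout to very high coverage together with imperfect linkage.

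**The case against.** Three stronger readings are tempting, and the documents do not support them.

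- A reader might infer that sections 7 and 9.1.1.3 flatly contradict each other. They describe different objects: the source registries and the linked table. The untested step is the transfer between them.
- A reader might infer that vaccination data are not checked at all. Coding, intervals and missing fields are checked; completeness is not.
- A reader might infer that the plan will produce spurious waning of a known size. No linkage rate or coverage is given. Annex 1 says linkage uses a unique identifier and 9.1.1.3 calls it compulsory, so s may be close to 1.

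The defence has further points. Section 9.1.1.3 restricts the study to people whose vaccination status can be established accurately, but it gives no criterion. Section 9.7.4.1 stratifies by calendar month and, if size allows, by region. That could expose a pattern, but it could not separate linkage loss from the confounding which the monthly analysis is meant to show. The head-to-head brand comparisons (9.1.1.5) do not use the unvaccinated pool, but they do not estimate VE against no vaccination. Data collection is due to end in July 2021 and section 9.5 dates general vaccination from 22 March 2021, so the late windows would hold little data until refreshes arrive. This limits the waning problem at first analysis but does not remove the level shift.

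Exact tables and thresholds could be left to an analysis plan. The point stands because the protocol itself rules out validation on a ground that does not apply to the linked exposure.

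**Conclusion.** The concern holds in a bounded form. The protocol declines to validate vaccination data on the strength of the source registries, says the sensitivity of the linked records is unknown, and plans nothing that would find an absent record. For any s below 1 the contaminated share rises with coverage and VE is biased toward zero; that direction follows from the design under the assumptions listed in the working. The size depends on assumed c and s. At 90% coverage and s of 0.95 to 0.99, the loss is 1.8 to 8.3 points from a true VE of 70% and 0.4 to 2.1 points from 95%. It is negligible at low coverage or near-perfect linkage. The relevant coverage is that within the matched age, sex and region cell, which can be high in prioritised age groups while overall coverage is low. Apparent waning is a conditional risk and should be reported as such.

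**What to change.** 1. In 9.1.1.3, add the kind of check already planned for infections. Compare cumulative first- and second-dose coverage in BIFAP with official coverage by region, age group, brand and calendar period. Official figures may come from the same link, so also compare with doses distributed, which 9.7.5 already mentions, as a more independent benchmark.
2. Judge a shortfall against the share still recorded as unvaccinated: f = (c − r)/(1 − r), where r = cs is recorded coverage. A fixed margin of 3 points would not do. At c = 90% and s = 0.97, r is 87.3%; the 2.7-point shortfall would pass, yet f = 2.7/12.7 = 21.3%. Allow for differences between up-to-standard BIFAP patients and the general population, since care-home residents and health workers are under-represented.
3. Add a sensitivity analysis that corrects each period-specific VE over a pre-stated range of s, using RR = RRobs(1−f)/(1−f·RRobs). Interpret the 91–180 and 181+ day windows in its light.
4. In section 7, limit the gold-standard statement to the source registries.

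The cost is one more comparison table and one bias analysis. Stopping comparator follow-up at a coverage threshold such as 80% should not be part of the fix, because it would remove the late follow-up on which the duration objective depends.
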